## **4.3 Clinical Laboratory Tests**

The study will collect laboratory data at baseline, Month 3 (limited laboratory data at Month 3), and Month 12. Laboratory data will be summarized by treatment group and time point by descriptive statistics.

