- Rivaroxaban has been studied for reduction of the risk of thrombotic cardiovascular (CV) events in patients with acute coronary syndrome (ACS) (ST segment elevation myocardial infarction, non-ST-segment elevation myocardial infarction, or unstable angina) in combination with acetylsalicylic acid (ASA) alone or with ASA plus a thienopyridine (clopidogrel or ticlopidine) in the ATLAS program. The ATLAS ACS 2 TIMI 51 study randomized a total of 15,526 subjects and demonstrated that rivaroxaban 2.5 mg or 5 mg twice daily compared with placebo reduced the risk of CV death, MI, or stroke by 16% in patients with a recent ACS, most of whom (92%) were also receiving dual antiplatelet therapy. The incidences of all categories of treatment-emergent bleeding were consistently higher in subjects treated with rivaroxaban compared with placebo. The higher rates of bleeding with rivaroxaban were expected, since in this study rivaroxaban was compared to placebo on the background of standard antiplatelet therapy.
- The MAGELLaN study compared VTE prophylaxis with oral rivaroxaban 10 mg once daily for 35 days with enoxaparin 40 mg daily for 10 days in subjects who were hospitalized for a medical illness. The MAGELLaN study randomized 8,101 subjects and met both of its primary efficacy objectives (ie, for rivaroxaban versus enoxaparin/placebo noninferiority at Day 10, and superiority at Day 35). Although bleeding rates in MAGELLaN were low overall, the incidences of clinically relevant bleeding events were increased in rivaroxaban treated subjects compared to enoxaparin.

In addition to bleeding, other adverse reactions associated with rivaroxaban include nausea, fever, kidney and liver impairment, dyspepsia, allergic reactions including skin reactions, itching, rash, hives, swelling of face, lips, mouth, tongue, skin or throat, and cholestasis.

Postmarketing data gathered subsequently to the pivotal studies do not change the favorable benefit-risk assessment of rivaroxaban in the approved indications.

For the most comprehensive description of the safety profile of rivaroxaban, refer to the latest version of the Investigator's Brochure for rivaroxaban.¹⁴

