1.2. Comparator Agent

Acetylsalicylic acid (ASA)

Acetylsalicylic acid is a nonsteroidal anti-inflammatory drug (NSAID). The mechanism of action of ASA is suppression of prostaglandins and thromboxanes production by irreversible inactivation of the cyclooxygenase enzyme required for prostaglandin and thromboxane synthesis.

Acetylsalicylic acid is indicated as a pain reliever for the temporary relief of minor aches and pains. It also has an antiplatelet effect and at lower doses can be used as a long-term treatment to help prevent heart attacks, strokes, and blood clot formation in patients at high risk of developing blood clots.

Adverse reactions associated with the use of ASA include allergic reactions, an increased risk of gastrointestinal bleeding, and Reye's syndrome.

Further information regarding low dose ASA can be found in the local approved product label.

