9.3.3. Other Safety Assessments

The safety and tolerability of rivaroxaban will also be evaluated by assessing other adverse events and clinical laboratory test values.

Any clinically relevant changes, including laboratory reports, occurring during the study must be recorded on the Adverse Event section of the eCRF. Any clinically significant abnormalities persisting at the end of the study/early withdrawal will be followed by the investigator until resolution or until a clinically stable endpoint is reached.

The study includes the evaluations of safety and tolerability according to the time points provided in the Time and Events Schedule.

Adverse Events

Adverse events will be reported by the parents/legally acceptable representatives for the duration of the study up to the Follow-Up Contact (30-days after last dose). Adverse events will be followed by the investigator as specified in Section 12, Adverse Event Reporting.

Clinical Laboratory Tests

The following tests results with reference ranges will be obtained at the visits specified in the Time and Events Schedule. Either hospital laboratory/local laboratory results or central laboratory results are acceptable at the time of study screening period. A central laboratory will be used during the rest of the study:

- Hematology Panel
 - hemoglobin
 - hematocrit
 - red blood cell (RBC) count^a
 - white blood cell (WBC)^b count
 - WBC differential^b:
 - neutrophils
 - lymphocytes
 - monocytes
 - eosinophils
 - basophils
 - platelet count
- Serum chemistry
 - creatinine (eGFR will be calculated using the original or the modified Schwartz formula for pediatric population, see [Attachment 3](#))²⁹
 - liver function tests (ALT, aspartate aminotransferase [AST], total and direct bilirubin, alkaline phosphatase)
- PT, aPTT tests

^a A RBC evaluation may include abnormalities in RBC count and/or RBC parameters (eg, reticulocyte count) and/or RBC morphology, which will then be reported by the laboratory

^b A WBC evaluation may include any abnormal cells, which will then be reported by the laboratory. In addition, any other abnormal cells in a blood smear will also be reported.

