12.3. Procedures

12.3.1. All Adverse Events

Adverse events should be reported by the subjects or their parents/legally acceptable representatives for the duration of the study.

For the purposes of this study, thrombotic events will be captured in the eCRF and in the database as efficacy outcomes only, and will not be reported as adverse events or serious adverse events, regardless of seriousness and severity, except for those thrombotic events that ended in death. All other thrombotic events will be exempted from expedited reporting.

Any serious adverse events other than thrombotic events will be reported to the sponsor in an expedited fashion according to Section 12.3.2, Serious Adverse Events.

All deaths (including those due to thrombotic causes) will be reported as serious adverse events.

All bleeding events will be collected on the eCRF as a bleeding event and as an adverse event or serious adverse event as appropriate. Serious bleeding events must be reported to the sponsor in an expedited manner as any other serious adverse events.

Certain adverse events are considered to be Adverse Events of Special Interest and should be reported as serious adverse events. These include:

- Suspected toxic effect on the bone marrow including severe thrombocytopenia (platelet count less than $50 \times 10^9/L$), severe neutropenia (white blood cell count less than $500/\mu L$), pancytopenia, aplastic anemia
- Suspected severe hypersensitivity reaction (eg, anaphylaxis, angioedema, severe urticaria, bronchospasm, etc.)
- Severe skin reactions such as Stevens-Johnson Syndrome
- Suspected severe liver injury and concurrent elevations of ALT $>5x$ ULN and total bilirubin $>2x$ ULN

All adverse events and special reporting situations, whether serious or nonserious, will be reported from the time a signed and dated ICF is obtained until completion of the subject's last study-related procedure (ie, Follow-Up Contact [phone contact]).

Serious adverse events, including those spontaneously reported to the investigator within 30 days after the last dose of study drug, must be reported via facsimile (fax) when applicable using the Serious Adverse Event page of the eCRF. The sponsor will evaluate any safety information that is spontaneously reported by an investigator beyond the time frame specified in the protocol.

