## **2. GENERAL ANALYSIS DEFINITIONS**

Statistical analysis of the overall study data will be done by the sponsor.

Description of the statistical methods to be used to analyze the efficacy and safety data is outlined in this document, including imputation rules for missing or partially missing dates.

Summaries by treatment group using appropriate descriptive statistics will be provided for study variables. Descriptive statistics such as mean, median, standard deviation, 95% CIs (when applicable), minimum, and maximum will be used to summarize continuous variables; Counts and percentages will be used to summarize categorical variables. The Kaplan-Meier (KM) method will be used to summarize time-to-event data. Graphical data displays may also be used to summarize the data.

For analysis purposes, the data from subjects receiving rivaroxaban in Part A of the study will be combined with the data from subjects in Part B of the study randomized to rivaroxaban. The data

will also be summarized separately for subjects randomized in Part B only (rivaroxaban vs. ASA), and for subjects participating in Part A only.

All CIAC adjudicated efficacy and bleeding outcomes will be used in the final analyses.

The statistical evaluation will be performed by using the software package SAS release 9.2 or higher (SAS Institute Inc., Cary, NC, USA).

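### SAP 4.3 specifies no by-arm count of children beyond the protocol's on-study liver and platelet limits, and its listed time points leave out ESMD and unscheduled laboratory values

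*SAP*

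**What the plan says.** SAP 4.3 is two sentences. Laboratory data are collected at baseline, Month 3 (a limited set) and Month 12, and "Laboratory data will be summarized by treatment group and time point by descriptive statistics". SAP 2 gives the general meaning for continuous variables: mean, median and standard deviation, and then "95% CIs (when applicable), minimum, and maximum will be used to summarize continuous variables". Section 4.3 names no count beyond a limit, no shift table and no worst post-baseline value.

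SAP 4.2 lists treatment-emergent events, treatment-emergent serious events, serious events starting more than 2 days after stopping, events leading to permanent discontinuation, and incidences by system organ class and preferred term. It has no special-interest category, although Protocol 12.3.1 creates one: "Certain adverse events are considered to be Adverse Events of Special Interest and should be reported as serious adverse events". The items there include "Suspected severe liver injury and concurrent elevations of ALT" above 5 times ULN with total bilirubin above 2 times ULN, and platelets below 50 x 10^9/L under suspected marrow toxicity.

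Protocol 9.3.3 says "The following tests results with reference ranges will be obtained at the visits specified", that eGFR will be calculated by a Schwartz formula, and that laboratory changes judged clinically relevant are to be recorded as adverse events. It also says "Either hospital laboratory/local laboratory results or central laboratory results are acceptable at the time of study screening period", with a central laboratory used afterwards.

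**The concern.** Protocol 1.1.3 says that "other adverse reactions associated with rivaroxaban include nausea, fever, kidney and liver impairment". Liver or platelet harm of this kind would be expected to show as a large change in a few children, not a small shift in all of them. The natural summary is therefore how many children in each arm crossed a fixed limit at any time after baseline. The plan instead summarizes the distribution at named visits. Two things are at stake in the Part B comparison:

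- A child who stops drug early, possibly because of a laboratory abnormality, has the closing sample at ESMD, a visit that SAP 4.3 does not list.
- Without a specified count, the by-arm evidence on liver and platelet harm rests on what investigators who know the treatment choose to report.

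**Working it through.** The plan gives no figure on this point to reproduce. There is no hypothesis test and no formal sample-size calculation (SAP 1.3, 1.4; Protocol Synopsis). About 90 children at 2:1 gives 60 on rivaroxaban and 30 on ASA.

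**1. Protocol schedule beside SAP 4.3** (hematology and chemistry; Time and Events Schedules and Attachment 1 note)

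| Time point | Part A | Part B | Listed in SAP 4.3 |
|---|---|---|---|
| Screening | both | both | yes, as baseline |
| Month 3 | chemistry only | none | yes |
| Month 12 | both | both | yes |
| ESMD | both | both | no |
| Unscheduled, for safety | if needed | if needed | no |

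Read as written, the randomized arms have one post-baseline laboratory time point, Month 12. The documents give no expected rate of early discontinuation, so the number of children affected cannot be stated. Each one is 1/60 = 1.7% of the rivaroxaban arm or 1/30 = 3.3% of the ASA arm.

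**2. Where each protocol limit is counted**

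| Limit | Protocol | Route to a by-arm count in the SAP |
|---|---|---|
| ALT >5x ULN with total bilirubin >2x ULN | 12.3.1, worded as suspected severe liver injury | SAE and preferred-term counts, if the investigator reports it |
| Platelets <50 x 10^9/L | 12.3.1, under suspected marrow toxicity; 10.2.1 as 50,000/µL, the same value | SAE and preferred-term counts, if reported |
| ALT >5x ULN alone | 10.2.1, the level on which the stopping consideration is built, with a condition on its course | Adverse-event counts only if recorded as an event; not of special interest |
| Hemoglobin fall of 2 g/dL or more with overt bleeding | 9.3.1 | Major bleeding, with 95% CI and Kaplan-Meier (SAP 4.1) |

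The fourth row is already covered. The first three have no count of measured values.

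**3. What a mean shows.** Assume a typical ALT of 0.6x ULN (not from the documents). One child at v x ULN shifts the arm mean by (v - 0.6)/n:

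- n = 60: (5.1 - 0.6)/60 = 0.075 and (10 - 0.6)/60 = 0.157x ULN.
- n = 30: (5.1 - 0.6)/30 = 0.15 and (10 - 0.6)/30 = 0.313x ULN.

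The planned maximum would show that child if the value fell at a listed visit. It would not say how many children crossed the limit, and it does not pair ALT with bilirubin.

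**4. What a count would give.** Clopper-Pearson 95% intervals; for zero cases the upper limit is 1 - 0.025^(1/n).

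| Cases | Rivaroxaban, n = 60 | ASA, n = 30 |
|---|---|---|
| 0 | 0 to 6.0% | 0 to 11.6% |
| 1 | 0.0 to 8.9% | 0.1 to 17.2% |
| 2 | 0.4 to 11.5% | 0.8 to 22.1% |

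For an assumed true rate p of 1% to 5%, the chance of at least one case, 1 - (1 - p)^n, is 0.45 to 0.95 with 60 children and 0.26 to 0.79 with 30.

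**5. Renal measure.** Attachment 3 gives eGFR = k x height / creatinine, so at constant eGFR creatinine rises in proportion to height. Assuming 5 to 8 cm of growth in a year from a starting height of 85 to 120 cm, the rise is between 5/120 = 4.2% and 8/85 = 9.4%. It should be similar in both randomized arms, so it mainly affects trends within an arm. SAP 4.3 names no renal measure, and SAP 2.4 lists creatinine clearance only as a baseline subgroup, whereas Protocol 4.2 (criterion 8.1) and 9.3.3 use eGFR.

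**The case against.** The strongest reply is that these harms already reach by-arm tables. Special-interest liver and platelet events are SAEs, clinically relevant laboratory changes are adverse events whenever they occur, and SAP 4.2 counts both and adds listings. Stopping because of such an event would also appear under events leading to discontinuation. This stands against a reading that a reader might draw from the SAP's silence, namely that these harms are never counted by arm. It does not replace a count of measured values: entry depends on whether an investigator who knows the treatment calls a change clinically relevant or suspects a cause, and ALT above 5x ULN alone is not a special-interest event.

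Three other inferences are tempting but not supported:

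- **A lost hemoglobin endpoint.** Protocol 1.2 names "an increased risk of gastrointestinal bleeding" for ASA, but a fall of 2 g/dL or more with overt bleeding is counted as major bleeding, and the protocol sets no limit for a fall without overt bleeding.
- **Creatinine analyzed unadjusted for growth.** SAP 4.3 does not say so, and Protocol 9.3.3 plans eGFR.
- **ALT above 3x and bilirubin above 1.5x ULN as harm limits.** In Protocol 4.2 they form part of one combined screening exclusion, with a direct-bilirubin condition.

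It can also be said that ESMD may be mapped to Month 12 in programming, since SAP 2.1 pairs the two for efficacy, and that table shells sit in the separate Data Presentation Specifications. Both are possible. But SAP 1 says that the SAP itself specifies key derived variables and methods, and a worst post-baseline value is a derived variable. The additional summaries mentioned in SAP 4.2 are optional.

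**Conclusion.** The gap is real but limited. As written, SAP 4.3 has no place for ESMD or unscheduled laboratory values, which matters most in Part B, where Month 12 is the only listed post-baseline time point with scheduled data. It also specifies no by-arm count of children beyond the protocol's liver and platelet limits. What remains is the adverse-event route, which is counted by arm but depends on open-label reporting. The primary safety outcome, major bleeding, is not affected.

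The size is qualitative. The documents give neither a discontinuation rate nor expected event rates, and the illustrations rest on the stated assumptions for typical ALT, event rate, height and growth. Table shells in the unseen specifications may already cover some of this. The SAP should be amended because its sample size is justified by the need for sufficient safety data and the better method uses values already collected.

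**What to change.** In SAP 4.3, add by treatment group the number and percentage of children, with exact 95% CI, whose worst post-baseline value, including ESMD and unscheduled samples:

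- exceeds ALT 5x ULN;
- meets ALT >5x ULN and total bilirubin >2x ULN concurrently;
- falls below platelets 50 x 10^9/L.

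Use the reporting laboratory's ULN, since screening results may be local. State how ESMD values enter the by-visit summary, and name Schwartz eGFR as the renal measure. Height is collected at Month 12 and ESMD but not at Part A Month 3, so the SAP should say which height is used there. In SAP 4.2, add a by-arm incidence line for the special-interest events of Protocol 12.3.1.

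The limits serve here for reporting only and no clinical rule changes. The cost is SAP wording and two or three tables from existing values, reference ranges and heights. The downside is small counts with wide intervals, which should be presented descriptively.

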## **4.4 Vital Signs and Physical Examination Findings**

Vital signs and physical examination findings will be summarized by treatment group and time point.

## **5. EFFICACY**

No formal hypothesis testing will be performed. The primary efficacy outcome will be any thrombotic event (venous or arterial), defined as:

- The appearance of a new thrombotic burden within the cardiovascular system on either routine surveillance or clinically indicated imaging, or
- The occurrence of a clinical event known to be strongly associated with thrombus (such as cardioembolic stroke, pulmonary embolism).

Subjects who develop either a symptomatic or asymptomatic thrombotic event during the study must permanently discontinue study drug. After cessation of study treatment, it is at the investigator's discretion to continue with other antithrombotic therapy. The investigator should document this therapy in the electronic case report form (eCRF). All available imaging results, e.g., transthoracic or transesophageal echocardiograms, or MRIs, relevant to a suspected thrombotic event should be sent to the CIAC for event adjudication. Thrombotic events will not be reported as adverse events or serious adverse events, as they will be reported as efficacy outcomes.

Transthoracic Echocardiograms will be obtained at screening, at Month 6 and Month 12 for the assessment of thrombotic events. For subjects who prematurely discontinue study drug for any reason (except when the child is enrolled because the local reader reviews the screening echo as without thrombosis and later on the central reviewer reports the presence of a thrombus), the final echocardiogram will be performed as soon as possible after discontinuation, at the ESMD visit. Investigators can image as often as medically necessary or as needed based on their institution's standard of care; however, protocol-based imaging must be performed at screening, Month 6 and at the end of therapy. Echocardiograms will be sent to a core laboratory for blinded reading and to minimize inter-site variability and bias.

The main efficacy description will be based on Full Analysis Set, excluding subjects who start on study drug but are discontinued if central reading by the core laboratory reports thrombosis on the Screening transthoracic echocardiogram (these subjects will be included however in the safety analysis) based on up-to-the-end-of-treatment period (outcomes confirmed by the CIAC).

Events that are reported after Month 12 or ESMD visit will be described in additional summaries or listings.

Additionally, data may also be summarized based on Full Analysis Set and up-to-last-FU (last contact) period or Per-protocol Analysis Set and On-treatment period.

Incidence rates (number of subjects with efficacy event during the period divided by number of subjects at risk at the beginning of the period) and the respective 95% CIs will be calculated for the primary efficacy outcome by treatment group.

Cumulative incidences (time to first event; Kaplan-Meier) will also be calculated for the efficacy outcomes.

In addition, listings of any efficacy outcomes will be provided.

Baseline demographics and disease characteristics relationship to thrombotic risk may be explored.

The numbers and percentages of subjects with missing Follow-Up Contact (30-days after last dose or Month 12) will be summarized.

All missing or partial data will be presented in the subject data listing as they are recorded on the eCRF.

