11. STATISTICAL METHODS

Statistical analysis will be done by the sponsor or under the authority of the sponsor. A general description of the statistical methods to be used to analyze the PK, PK/PD, safety, and the efficacy data is outlined below. Specific details will be provided in the Statistical Analysis Plan (SAP), including, if necessary, censoring rules for time-to-event analyses and imputation rules for missing or partially missing dates.

The SAP will be finalized prior to first subject enrolled in the study.

Data from subjects participating in Part A of the study are planned to be combined with data from subjects in Part B of the study who were randomized to rivaroxaban. Summaries will also be provided based on data from: (a) randomized subjects only (rivaroxaban vs. ASA) from Part B, and (b) subjects participating in Part A only.

For both parts of the study, safety and efficacy results (adverse events, bleedings, and thrombotic events) will be summarized. All summaries will be presented using appropriate descriptive statistics for study variables including demographic and baseline characteristics. Descriptive statistics such as mean, median, standard deviation, minimum, and maximum will be used to summarize continuous variables. Counts and percentages will be used to summarize categorical variables.

The best available data for safety events will be used by the DRC and IDMC to review subjects in the Initial PK, PD, and Safety Assessment Period of Part A. The CIAC-adjudicated results will be used in the final analysis for all subjects.

No statistical hypothesis will be tested in this study.

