11.5. Efficacy Analysis

Efficacy analyses will be performed on the Full Analysis Set, excluding subjects who start on study drug but are discontinued if central reading by the core laboratory reports thrombosis on the Screening transthoracic echocardiogram. These subjects will be included however in the safety analysis. Thrombotic events that occur during the Up-to-End-of-Treatment Period will be summarized by treatment received. Events that occur after Up-to-End-of-Treatment Period (after Month 12 or ESMD visit) will be summarized separately.

The efficacy outcomes will be adjudicated by CIAC.

The numbers and percentages of subjects with missing Follow-Up Contact (30-days after last dose) will be summarized. Details will be provided in the SAP.

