## **2.2 Analysis Sets**

Full Analysis Set: This analysis set consists of all subjects in Part A who receive at least 1 dose of study drug and all subjects in Part B who are randomized and receive at least 1 dose of study drug.

Safety Analysis Set: This is the same as Full Analysis Set.

Per-protocol Set: The per-protocol set will exclude subjects with key protocol deviations from full analysis set. These deviations will include the following:

- Not meeting the following key inclusion or exclusion criteria:
  - INT-1: inclusion criteria 1, exclusion criteria 1, 4, 6 (> 90 consecutive days), 7, 8, 13, 14, 15, 18
  - INT-2: inclusion criteria 1, exclusion criteria 1, 4, 6 (> 90 consecutive days), 7, 8.1, 13, 14, 15, 18
- Taking incorrect study drug
- Not discontinuing study drug permanently according to the protocol
- Having been taking prohibited concomitant therapies as specified in the protocol

PK Analysis Set: All subjects who receive at least 1 dose of study drug and have quantifiable rivaroxaban plasma concentrations will be included in the descriptive PK analysis.

PD Analysis Set: All subjects who receive at least 1 dose of study drug and have quantifiable and time-matched PT, aPTT, and/or anti-FXa activity values will be included in the descriptive PD analysis.

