## **3. SUBJECT INFORMATION**

Summary statistics (arithmetic mean, standard deviation, median, minimum and maximum for quantitative variables) will be presented by treatment. Frequency tables for qualitative data will be provided. No statistical tests will be performed to compare these characteristics across treatment groups. Unless stated otherwise, all subject information summaries will be based on safety analysis set and will be presented for rivaroxaban combined from Parts A and B, ASA and rivaroxaban from Part B, and rivaroxaban from Part A.

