## 4.1 Bleeding Events

The primary safety outcome is the major bleeding events, as defined below. Clinically relevant non-major bleeding events and trivial (minimal) bleeding will be secondary safety outcomes.

Bleeding events will be adjudicated by the CIAC using the International Society on Thrombosis and Hemostasis (ISTH) recommendations (Buller 2007, Schulman 2005).

Major bleeding is defined as overt bleeding and:

- Associated with a fall in hemoglobin of 2 g/dL or more; or
- Leading to a transfusion of the equivalent of 2 or more units of packed red blood cells or whole blood in adults; or
- Occurring in a critical site: intracranial, intraspinal, intraocular, pericardial, intra-articular, intramuscular with compartment syndrome, retroperitoneal; or
- Contributing to death.

Clinically relevant non-major bleeding is defined as overt bleeding not meeting the criteria for major bleeding but associated with:

- Medical intervention, or
- Unscheduled contact (visit or telephone call) with a physician, or
- (Temporary) cessation of study treatment, or
- Discomfort for the subject such as pain, or
- Impairment of activities of daily life (such as loss of school days or hospitalization).

Trivial (minimal) bleeding is defined as any other overt bleeding event that does not meet criteria for clinically relevant non major bleeding.

The main description will be based on Safety Analysis Set during the On-treatment period (bleeding events confirmed by the CIAC).

Incidence rates (number of subjects with bleeding event during the period divided by the number of subjects at risk at the beginning of the period) and the respective 95% CIs will be calculated for the major and clinically relevant non major bleedings by treatment group. Cumulative

incidence rates (time to first event; Kaplan-Meier) will be calculated for the major bleeding and clinically relevant non-major bleeding.

In addition, listing for all bleedings will be provided, including those that are reported more than 2 days after stop of study medication.

Baseline demographics and disease characteristics relationship to bleeding risk may be explored.

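### Do the main efficacy and bleeding descriptions let non-randomised Part A children into the comparison with ASA?

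*SAP*

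**What the plan says.** **Main descriptions.** SAP 5: "The main efficacy description will be based on Full Analysis Set", less children whose screening echocardiogram shows thrombosis on central reading, over the period up to end of treatment. SAP 4.1, for bleeding: "The main description will be based on Safety Analysis Set during the On-treatment period".

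**Who is in the set.** SAP 2.2, on the Full Analysis Set: "This analysis set consists of all subjects in Part A who receive at least 1 dose of study drug", together with treated, randomised Part B subjects. The Safety Analysis Set is defined as the same set.

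**How the parts are displayed.** Protocol 11: "Data from subjects participating in Part A of the study are planned to be combined with data from subjects in Part B" who were randomised to rivaroxaban. It then promises summaries of the randomised Part B subjects (rivaroxaban against ASA) and of Part A alone. SAP 2 has the same rule: after the pooling sentence, the data "will also be summarized separately for subjects randomized in Part B only (rivaroxaban vs. ASA"), and Part A is also shown on its own. For subject information, SAP 3 lists the columns: summaries "will be presented for rivaroxaban combined from Parts A and B, ASA and rivaroxaban from Part B, and rivaroxaban from Part A".

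**Grouping of efficacy events.** Protocol 11.5: "Thrombotic events that occur during the Up-to-End-of-Treatment Period will be summarized by treatment received". SAP 5: incidence rates and their confidence intervals "will be calculated for the primary efficacy outcome by treatment group".

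**The concern.** Comparison with ASA is the primary objective of Part B (Protocol 2.1, SAP 1.1), and Protocol 3.2 gives the validity of the descriptive comparison as a reason for randomising. Yet SAP 4.1 and 5 attach the word *main* to a set that includes Part A, and the Part B comparison comes second, under *also*. The column list in SAP 3 is not repeated for bleeding or efficacy.

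Part A children differ from Part B children by design:

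- They have no concurrent ASA group, because Part B enrolment starts after Part A enrolment ends (Protocol 9.1.3.2).
- Some exclusion criteria apply to one part only (Protocol 4.2, criteria 10.1 and 15).
- The internal review committee can withdraw a child after the initial period (Protocol 10.3).
- The IDMC had the option of adjusting the Part B dose (Protocol 3.1).

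In an open-label study with few events, freedom to choose which rivaroxaban figure stands beside ASA after the results are known would be a real weakness. The differing words on grouping in Protocol 11.5 and SAP 5 seem to add a second ambiguity.

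**Working it through.** **1. What *main* ranks.** Set the SAP's statements side by side.

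| Place | Main | Contrasted with |
|---|---|---|
| SAP 5 | Full Analysis Set less the core-laboratory exclusions, up to end of treatment | Optional: Full Analysis Set to last contact; per-protocol set on treatment |
| SAP 4.1 | Safety Analysis Set, on treatment | Listing that also covers bleeds more than 2 days after stopping |

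Every contrast is one of analysis set or period. None is between pooled rivaroxaban and Part B rivaroxaban. That choice is made once, for all summaries, in SAP 2.

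**2. Which comparison with ASA is committed to.** Of the three displays in SAP 2 and Protocol 11 (pooled rivaroxaban, Part B, Part A), only the Part B display is labelled as rivaroxaban versus ASA. SAP 3 also pairs ASA with Part B rivaroxaban. Neither document names a contrast of pooled rivaroxaban with ASA. An analyst following the plan must produce the randomised comparison.

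**3. Numbers.** The plan's own total reproduces: about 10 (Part A) + about 90 (Part B) = 100 (SAP 1.4). The 2:1 ratio (Protocol 5, SAP 1.5) gives 90 × 2/3 = 60 rivaroxaban and 90 × 1/3 = 30 ASA. Pooled rivaroxaban is 60 + 10 = 70, and the Part A share is 10/70 = 14.3%.

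The documents give no expected event count for this trial, so the counts below are assumptions. Intervals are exact (Clopper-Pearson) 95%; the SAP names no interval method.

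| Part B rivaroxaban | Part A events (of 10) | Pooled rivaroxaban | Shift, points |
|---|---|---|---|
| 6/60 = 10.0% (3.8 to 20.5) | 0 | 6/70 = 8.6% (3.2 to 17.7) | −1.4 |
| 6/60 | 1 | 7/70 = 10.0% (4.1 to 19.5) | 0.0 |
| 6/60 | 3 | 9/70 = 12.9% (6.1 to 23.0) | +2.9 |
| 3/60 = 5.0% (1.0 to 13.9) | 0 | 3/70 = 4.3% (0.9 to 12.0) | −0.7 |
| 3/60 | 3 | 6/70 = 8.6% (3.2 to 17.7) | +3.6 |

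Difference from an assumed 3/30 = 10.0% on ASA (Newcombe 95% intervals where given):

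- 6/60: 0.0 (−16.5 to 12.1). Pooled: −1.4 (−17.7 to 9.6) with no Part A events, +2.9 (−13.9 to 14.6) with three.
- 3/60: 5.0 − 10.0 = −5.0. Pooled: 4.3 − 10.0 = −5.7 with no Part A events, 8.6 − 10.0 = −1.4 with three.

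In the first scenario the sign can go either way only because the Part B difference was set at exactly zero. In the second it does not change. Three events in 10 Part A children is the extreme end of the range.

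**4. Grouping words.** SAP 4.1 also says by treatment group for bleeding, where Protocol 11.4 says treatment group as received. The SAP phrase is therefore a generic label that leaves the Protocol's rule standing, not a competing rule. The two readings give different figures only if a child takes a drug other than the one assigned. SAP 2.2 lists that as a key deviation, and SAP 3.6 has such deviations summarised.

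**5. Dosing.** The Part B dose adjustment was one option open to the IDMC. Protocol 6, Table 1, gives a single rivaroxaban dosing table with no split by part, so nothing in the current text shows the two parts being dosed differently.

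**The case for a change.** The strongest case for a change is that the SAP does rank its analyses and leaves only the Part A/Part B dimension unranked. It shows in SAP 3 that it can write the column list, but does not repeat it where it matters most. The study tests nothing, so point estimates and the choice of lead table carry the message. A sentence in SAP 4.1 and 5 would cost almost nothing: if the lead rivaroxaban estimate rested on 60 rather than 70 children, its interval at a 10% rate would be 16.7 points wide (6/60) instead of 15.4 (7/70), and the pooled figure would still be reported.

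Part of this stands. No sentence calls the Part B comparison the main one, and one that did would be harmless. But the gap is one of ranking, not of a missing analysis. The general rule in SAP 2 already covers bleeding and efficacy, so leaving out the column list there does not remove the Part B display. Table titles and mock-ups sit in the separate Data Presentation Specifications (SAP 1), so these documents alone cannot show that the order of tables is open. Replacing treatment received with the randomised arm in Protocol 11.5 would go beyond clarification: it would alter a stated rule and need a formal amendment (Protocol 17.1).

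**Conclusion.** The concern does not call for a change. The set behind the main descriptions does include Part A, and the Part B comparison is not labelled as main. But the randomised comparison is committed to in both documents, it is the only contrast with ASA that is named, and the trial objectives assign the comparison to Part B. A statistician following the plan produces it without having to choose.

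If pooled rivaroxaban were nevertheless set beside ASA, the rate would move by −1.4 to +2.9 points from an assumed 6/60, or by −0.7 to +3.6 points from an assumed 3/60. The exact intervals around those two Part B rates are 16.7 and 12.9 points wide. No test, error rate or margin is affected. The grouping wording has no effect unless a child takes the wrong drug.

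This rests on about 10 children in Part A, about 90 in Part B split 2:1, illustrative event counts, and the one dosing table applying to both parts. A sentence ranking the displays would be a courtesy to the reader; it would add no analysis and alter no result.
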